8.3.9 Brief Medication Questionnaire

Brief medication questionnaire results will be summarized for the number and percentage of patients reporting:

- each medication taken
- each indication
- combination of medication taken per indication
- compliance for each medication taken

Descriptive summary tables will be presented separately for Group A and Group B. Summary tables and listings for brief medication questionnaire will only be based on data from MIV-711-202 study.

9. Safety Analysis

For the safety outcomes, for study Group A, changes from baseline will be assessed using the Visit 2 baseline data from MIV-711-201. For study Group B, changes from baseline will be assessed using the Visit 2 data from Study MIV-711-202.

The change from baseline for visit X will be calculated as the (visit X – baseline visit)-difference in observed values. Note that the change from baseline will be calculated for all visits in study MIV-711-201 and study MIV-711-202 where the actual endpoint has been observed, i.e. not only for visits in study MIV-711-202 succeeding the baseline visit.

All safety summary tables will be based on the SAF population.

Descriptive summaries for safety will be presented by study group and visit, as appropriate.

PAREXEL International Statistical Analysis Plan

Medivir
Protocol: MIV-711-202

Final 1.0
16 January 2018

9.1 Adverse Events

All AEs reported will be coded and classified according to MedDRA version 18.1. A treatment-emergent AE (TEAE) will be defined as an AE that begins or that worsens in severity after IMP has been administered.

Non-treatment emergent adverse events (NTEAE): AEs that occurred before the administration of IMP and did not worsen in severity or relationship after exposure to IMP.

All AE data as captured on the CRF for MIV-711-202 study will be listed by patient. All AEs from MIV-711-201 study for those patients admitted into the MIV-711-202 study will also be listed. All serious AEs (SAEs) will be listed. A listing of all AEs leading to treatment discontinuation will be presented.

Unless specified otherwise, all adverse event summaries will include the TEAEs only and adverse event summary counts of AEs will be the number of patients reporting adverse events and not the number of events reported. The number and percentage of patients with adverse events will be tabulated by body system (SOC) and preferred term (PT) for each group (A, B) and study (MIV-711-201, MIV-711-202). A patient with multiple adverse events within a body system is only counted once towards the total of that body system. If the same AE (preferred term) is reported several times for the same patient, it will only appear once for that specified treatment in the summary tables.

For patients with multiple adverse events of the same preferred term and of different severities, the AE with the highest assessment of severity will be used in the summaries presented by severity.

A general summary of all treatment-emergent adverse events will show the number and percentage of patients, as well as the number of events, according to the following categories:

- All treatment emergent adverse events
- ‘Related’ treatment emergent adverse events
- Mild treatment emergent adverse events
- Moderate treatment emergent adverse events
- Severe treatment emergent adverse events
- Serious treatment emergent adverse events
- Treatment emergent adverse events leading to early termination
- Deaths

Other summary tables for adverse events will include:

PAREXEL International Statistical Analysis Plan

Medivir
Protocol: MIV-711-202

Final 1.0
16 January 2018

- Number and Percentage of Patients with Treatment Emergent Adverse Events by System Organ Class, and Preferred Term
- Number and Percentage of Patients with Treatment Emergent Adverse Events ‘Related to IMP’ by System Organ Class, Preferred Term, and Severity.
- Number and Percentage of Patients with Serious Treatment Emergent Adverse Events by System Organ Class, and Preferred Term
- Number and Percentage of Patients with Treatment Emergent Adverse Events Leading to Discontinuation by System Organ Class, and Preferred Term
- Number and Percentage of Patients with Treatment Emergent Adverse Events by Preferred Term per Frequency of Occurrence

All AE summary tables will display the AEs that occurred in both MIV-711-201 and MIV-711-202 studies for patients that were dosed in MIV-711-202. For tabulations of AEs by study group, any AE that starts on or after administration of the first dose received in MIV-711-201 and before the first dose received in MIV-711-202, will be assigned to the the 201 study group. Any AE occurring after the first dose administered in MIV-711-202 will be assigned to the 202 study group.

If a subject has multiple AEs with the same preferred term but occurring after each dose administration (MIV-711-201 and MIV-711-202), then one AE will be counted for each treatment administration. Adverse events that emerge in the first treatment period (201) and carry over into the next period (202) will be attributed to only the period in which the AE emerged (201). Such AEs that carry over into MIV-711-202 will be recorded as part of MIV-711-202 medical history.

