## 9.5 Statistical Methodology

### 9.5.1 Primary Endpoint (Study Population A)

The primary outcome will be to study the safety and tolerability of 200 mg MIV-711 q.d. over 52 (26+26) weeks in patients with symptomatic and radiographic knee OA.

Safety endpoints:

- Incidence and severity of AEs
- Incidence and severity of clinical laboratory abnormalities
- Physical examination findings by patient
- Incidence and severity of ECG abnormalities
- Mean change from Baseline (Visit 2 of Study MIV-711-201) in vital signs (blood pressure, heart rate, temperature) and oxygen saturation
- Categorical summary of observed vital signs and vital sign changes compared to Baseline (Visit 2 of Study MIV-711-201), by patient

Safety and tolerability will be assessed descriptively in summary tables presented over time. All data presentations addressing the primary outcome will use Study Population A.

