### **9.5.4 Safety**

The primary purpose and endpoint of the present study is safety and tolerability as described above. There will be no formal statistical hypothesis testing for safety data in this study, therefore only summary statistics will be provided. Safety summaries will be presented by scheduled assessment for the SAF. Summary statistics (number of observations, mean, SD, median, minimum and maximum values) will be presented for continuous variables, and number and percentages (n, %) will be presented for categorical variables. Where applicable, changes from Baseline will also be summarised over time.

Treatment-emergent adverse events will be summarised by preferred term and system organ class and classified according to the latest version of coded Medical Dictionary for Regulatory Activities (MedDRA). The number and percentage of TEAEs will be summarised by system organ class and preferred term in the SAF. Treatment-emergent adverse events will be further summarised with respect to severity and relationship to IMP. Treatment-emergent adverse events related to IMP, leading to withdrawal, serious TEAEs, and deaths will be summarised.

Clinical laboratory tests (haematology, serum chemistry), ECG, and vital signs will be summarised for the SAF at each scheduled assessment. Potentially clinically important findings will also be summarised and listed.

The number of patients taking rescue medication (see definition in Section 6.6.1), the amount of rescue medication taken and the reason for use will be tabulated and summarised descriptively.

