Number and Percentage of Patients with Treatment Emergent Adverse Events
by System Organ Class, Preferred Term, and Group
SAF Population

System Organ Class Preferred Term	MIV-711-201			MIV-711-202		
	Group A 26 weeks N = x	Group B 26 weeks N = x	Overall N = x	Group A 26 weeks N = x	Group B 26 weeks N = x	Overall N = x
System Organ Class 1	nn (nn.n%)	nn (nn.n%)	nn (nn.n%)	nn (nn.n%)	nn (nn.n%)	nn (nn.n%)
Preferred Term 1	nn (nn.n%)	nn (nn.n%)	nn (nn.n%)	nn (nn.n%)	nn (nn.n%)	nn (nn.n%)
Preferred Term 2	nn (nn.n%)	nn (nn.n%)	nn (nn.n%)	nn (nn.n%)	nn (nn.n%)	nn (nn.n%)
Preferred Term 3	nn (nn.n%)	nn (nn.n%)	nn (nn.n%)	nn (nn.n%)	nn (nn.n%)	nn (nn.n%)
Preferred Term xx	nn (nn.n%)	nn (nn.n%)	nn (nn.n%)	nn (nn.n%)	nn (nn.n%)	nn (nn.n%)
System Organ Class 2	nn (nn.n%)	nn (nn.n%)	nn (nn.n%)	nn (nn.n%)	nn (nn.n%)	nn (nn.n%)
Preferred Term 1	nn (nn.n%)	nn (nn.n%)	nn (nn.n%)	nn (nn.n%)	nn (nn.n%)	nn (nn.n%)
Preferred Term 2	nn (nn.n%)	nn (nn.n%)	nn (nn.n%)	nn (nn.n%)	nn (nn.n%)	nn (nn.n%)
Preferred Term 3	nn (nn.n%)	nn (nn.n%)	nn (nn.n%)	nn (nn.n%)	nn (nn.n%)	nn (nn.n%)
Preferred Term xx	nn (nn.n%)	nn (nn.n%)	nn (nn.n%)	nn (nn.n%)	nn (nn.n%)	nn (nn.n%)

PAREXEL International SAP Amendment Shells

Medivir
Protocol: MIV-711-202

Final 1.0
16 January 2018

Medivir
Protocol Number: MIV-711-202

Page X of Y

Table 14.3.1.3
Number and Percentage of Patients with Treatment Emergent Adverse Events 'Related to IMP'
by System Organ Class, Preferred Term, Severity, and Group
SAF Population

		MIV-711-201			MIV-711-202			
System Organ Class	Preferred Term	Group A 26 weeks N = x	Group B 26 weeks N = x	Overall N = x	Group A 26 weeks N = x	Group B 26 weeks N = x	Overall N = x	
	Severity							
System Organ Class 1	Mild	nn (nn.n%)	nn (nn.n%)	nn (nn.n%)	nn (nn.n%)	nn (nn.n%)	nn (nn.n%)	
	Moderate	nn (nn.n%)	nn (nn.n%)	nn (nn.n%)	nn (nn.n%)	nn (nn.n%)	nn (nn.n%)	
	Severe	nn (nn.n%)	nn (nn.n%)	nn (nn.n%)	nn (nn.n%)	nn (nn.n%)	nn (nn.n%)	
	Preferred Term 1	Mild	nn (nn.n%)	nn (nn.n%)	nn (nn.n%)	nn (nn.n%)	nn (nn.n%)	nn (nn.n%)
		Moderate	nn (nn.n%)	nn (nn.n%)	nn (nn.n%)	nn (nn.n%)	nn (nn.n%)	nn (nn.n%)
		Severe	nn (nn.n%)	nn (nn.n%)	nn (nn.n%)	nn (nn.n%)	nn (nn.n%)	nn (nn.n%)
	Preferred Term xx	Mild	nn (nn.n%)	nn (nn.n%)	nn (nn.n%)	nn (nn.n%)	nn (nn.n%)	nn (nn.n%)
		Moderate	nn (nn.n%)	nn (nn.n%)	nn (nn.n%)	nn (nn.n%)	nn (nn.n%)	nn (nn.n%)
		Severe	nn (nn.n%)	nn (nn.n%)	nn (nn.n%)	nn (nn.n%)	nn (nn.n%)	nn (nn.n%)

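### Severity is tabulated by preferred term only for adverse events rated related, so no summary table shows which unrelated terms were severe

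*SAP*

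**What the plan says.** Protocol 7.1 and 9.5.1 list "Incidence and severity of AEs" among the primary safety endpoints, and 9.5.1 has them assessed descriptively in summary tables. Protocol 9.5.4 first plans TEAEs by system organ class (SOC) and preferred term (PT), and then adds: "Treatment-emergent adverse events will be further summarised with respect to severity and relationship to IMP". Neither section limits the severity summary to related events.

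SAP 9.1 plans a general summary and five tables by term:

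- The general summary counts patients and events in categories, one of which is "Severe treatment emergent adverse events". It covers all TEAEs but names no terms.
- The main table by term is "Number and Percentage of Patients with Treatment Emergent Adverse Events by System Organ Class, and Preferred Term". It has no severity split.
- The table that does split by severity carries, in its shell (Table 14.3.1.3), the title "Number and Percentage of Patients with Treatment Emergent Adverse Events 'Related to IMP"; SAP 9.1 specifies it "by System Organ Class, Preferred Term, and Severity".
- Serious events and events leading to discontinuation each have a table by SOC and PT, without severity: "Number and Percentage of Patients with Serious Treatment Emergent Adverse Events by System Organ Class, and Preferred Term" and "Number and Percentage of Patients with Treatment Emergent Adverse Events Leading to Discontinuation by System Organ Class, and Preferred Term".
- A last table orders all TEAEs by frequency of preferred term, again without severity.

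SAP 9.1 also lists every AE by patient, from both studies.

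**The concern.** Relatedness is a two-category judgement (related or unrelated) made by the investigator (Protocol 7.13.2.3). In MIV-711-202 it is made knowing that every patient takes 200 mg, and there is no concurrent control group to show the background rate of an event. Using that judgement to decide which events get their severity shown by term lets an unblinded opinion filter the only term-level severity table for a primary endpoint.

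The tables for serious events and for discontinuations do not fill the gap. Neither shows severity, and severity and seriousness are defined separately: intensity is graded by interference with usual activities (Protocol 7.13.2.2), whereas seriousness follows outcome criteria such as death or hospitalisation (Protocol 7.13.2.1). A severe event can be non-serious and need not stop treatment. Protocol 7.13.2.4 sets no adverse events of special interest, so no separate summary would pick such events up. At stake is whether a reader of the tables can tell if the severe events judged unrelated are scattered over many terms or concentrated in one.

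**Working it through.** No sample size, power or error rate is involved, so the check is a cross-reading. The inputs are the tables named in SAP 9.1, the table list in SAP 11, the shells in SAP 14 and the listing shells in SAP 15.

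**Step 1. What each AE table carries.**

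| Table | TEAEs covered | Preferred term | Severity |
|---|---|---|---|
| 14.3.1.1 | all | no | yes (mild, moderate and severe totals) |
| 14.3.1.2 | all | yes | no |
| 14.3.1.3 | related only | yes | yes |
| 14.3.1.4 | serious, any relationship | yes | no |
| 14.3.1.5 | leading to discontinuation, any relationship | yes | no |
| 14.3.1.6 | all | yes | no |

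Two tables carry severity and five carry preferred terms. Every one of the six carries at least one of the two, so the number carrying both is 2 + 5 − 6 = 1. That one is Table 14.3.1.3, and it covers related events only. The number crossing term with severity for all TEAEs is 0.

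**Step 2. Follow one severe, unrelated TEAE.** It adds to the severe row of 14.3.1.1 with no term attached. It adds to its term in 14.3.1.2 and 14.3.1.6 with no severity attached. If it is serious it also enters 14.3.1.4, and if it leads to discontinuation, 14.3.1.5; neither gives severity. It does not enter 14.3.1.3.

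**Step 3. Can the missing cell be found by subtraction?** For a given term, let n be the patients in 14.3.1.2 and r(mild), r(moderate), r(severe) the patients in 14.3.1.3, each patient counted once per term. Then

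n − [r(mild) + r(moderate) + r(severe)] = patients whose events under that term were all rated unrelated.

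This gives how many such patients there are, but not how severe their events were. The severe row of 14.3.1.1 is summed over all terms and over both relationship categories, so it cannot be allocated to terms. Subtraction therefore fails, unless 14.3.1.1 shows no severe events at all.

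**Step 4. Where the information does exist.** The shell of Listing 16.2.7.1 has columns for preferred term, SOC, severity and relationship. Listings 16.2.7.2 and 16.2.7.3 do the same for serious events and for discontinuations.

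**Step 5. Which columns the open-label argument covers.** Each AE table has MIV-711-201 and MIV-711-202 columns. The first set comes from a double-blind, placebo-controlled study, and Group B was on placebo in that period. Only the second set rests on open-label, uncontrolled judgements. The table gap itself affects both sets.

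**The case against.** The sponsor can fairly say the following.

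- **Severity is summarised for all TEAEs.** Table 14.3.1.1 gives mild, moderate and severe counts irrespective of relationship. A reader might infer that severity is described only for related events; that is not so.
- **Unrelated events appear under their terms.** A reader might infer that a severe unrelated event shows in no table with its term, or that a cluster of such events would be invisible. Tables 14.3.1.2 and 14.3.1.6 contradict this: the events are counted under their term. Only the link from term to grade is missing.
- **The protocol is not clearly breached.** Protocol 9.5.4 does not say in terms that severity is to be crossed with preferred term, and Table 14.3.1.1 could be held to meet it literally. The sentence does come straight after the one on SOC and PT and begins by adding to it, so a term-level reading is the more natural, but it is not the only one.
- **The study is small and descriptive.** Protocol 5.4 expects about 50–80 patients, 9.2.1 states no confirmatory power and 9.5.4 no safety testing. Searching a listing of that size is feasible.

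All four points stand and limit the concern. They do not remove it: totals without terms do not say which events were severe, and a by-patient listing is not the summary table that Protocol 9.5.1 calls for.

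**Conclusion.** The point holds in a limited form. Among the six AE tables, severity is crossed with preferred term only where the investigator rated the event related, although the primary endpoint concerns the severity of all AEs and Protocol 9.5.4 does not make the severity summary depend on relationship. For unrelated TEAEs, no summary table shows which terms were severe.

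The gap applies to every TEAE rated unrelated, in both groups and both studies. It cannot be given as a percentage, because the documents do not state what share will be rated unrelated. If there are no severe events, or all of them are rated related, no severe event goes unnamed. The argument that relatedness is an unblinded filter applies to the MIV-711-202 columns only; a reader might extend it to the MIV-711-201 columns, but the double-blind design of that study does not support this.

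This is a gap in display, not a loss of data. It is worth closing because it concerns a primary endpoint and the remedy needs nothing new. The conclusion assumes that the table list and shells in the SAP are the complete set of planned AE tables.

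**What to change.** Add to SAP 9.1, the table list and the shells a table of all TEAEs by SOC, preferred term and maximum severity, by group and study, irrespective of relationship. Keep Table 14.3.1.3 for related events as a second display.

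The shell of 14.3.1.3 can be reused with the relatedness filter removed. SAP 9.1 already has the rule the table needs: a patient with several events of the same preferred term is counted at the highest severity. The cost is one repeat run of an existing table program. No new data, derivation or protocol change is required.

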## 7 ENDPOINT AND METHODS OF ASSESSMENT

### 7.1 Primary Endpoint (Study Population A)

The primary objective is to study the safety and tolerability of MIV-711 in OA patients who have received treatment for up to 52 (26+26) weeks.

Safety endpoints:

- Incidence and severity of AEs
- Incidence and severity of clinical laboratory abnormalities
- Physical examination findings by patient
- Incidence and severity of ECG abnormalities
- Mean change from Baseline (Visit 2 of Study MIV-711-201) in vital signs (blood pressure, heart rate, temperature) and oxygen saturation
- Categorical summary of observed vital signs and vital sign changes compared to Baseline (Visit 2 of Study MIV-711-201), by patient

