2.1 Primary Objective Study Group A

To assess the safety and tolerability of 200 mg MIV-711 q.d. over 52 (26+26) weeks in patients with symptomatic and radiographic knee osteoarthritis.

- Study Group A will be recruited from patients treated with 200 mg MIV-711 q.d. in Study MIV-711-201 and whose symptoms did not clinically significantly deteriorate as defined by an increase in NRS of ≤ 2 compared to Baseline.

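### The AE tables count Group A patients separately in study 201 and study 202, so for rows filled in both they only bound patient incidence over the 52 (26+26) weeks of the primary objective

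*SAP*

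**What the plan says.** SAP 2.1 gives the primary objective for Group A: "To assess the safety and tolerability of 200 mg MIV-711 q.d. over 52 (26+26) weeks". Protocol 7.1 lists "Incidence and severity of AEs" first among the endpoints for that objective. Protocol 9.5.1 adds: "All data presentations addressing the primary outcome will use Study Population A".

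SAP 9.1 sets the counting rules:

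- Scope: "All AE summary tables will display the AEs that occurred in both MIV-711-201 and MIV-711-202 studies for patients that were dosed in MIV-711-202".
- The number and percentage of affected patients "will be tabulated by body system (SOC) and preferred term (PT) for each group (A, B) and study (MIV-711-201, MIV-711-202").
- An AE that starts on or after the first 201 dose and "before the first dose received in MIV-711-202, will be assigned to the the 201 study group"; later AEs go to 202. An AE that starts in 201 and carries over is counted in 201 only.
- If a patient has the same preferred term after dosing in each study, "then one AE will be counted for each treatment administration".
- Listings: "All AEs from MIV-711-201 study for those patients admitted into the MIV-711-202 study will also be listed".

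All six AE shells (Tables 14.3.1.1 to 14.3.1.6) follow this layout. Each study block has a Group A, a Group B and an Overall column, with the group columns labelled as 26 weeks. The table list in SAP 11 contains no other AE table.

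Two other places matter. SAP 9.2.1 takes the laboratory minimum and maximum over all post-baseline visits on 200 mg, which for Group A covers both studies. SAP 11 puts the dosing Tables 14.1.8 and 14.1.9 on the PPS, whereas SAP 9 puts all safety summaries on the SAF.

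**The concern.** The natural summary for the primary objective is the number of Group A patients who had a given AE at least once from their first 200 mg dose onwards. The two blocks hold the same patients, and the tables do not report how many were affected in both. Their patient counts cannot be added, so the headline figure for the first-listed endpoint would have to be counted by hand from the listings.

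Three related features make the tables easy to misread:

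- The 201 Overall column pools Group A on 200 mg with Group B on placebo, so it describes no single treatment.
- The 201 columns hold only patients who finished 201 Visit 8 and rolled over. Zeros for deaths and discontinuations there follow from selection and are not a finding about the 200 mg arm. The shells carry no footnote saying so.
- The dosing tables that accompany the safety results use a set that by rule leaves out discontinued patients and those who missed more than 7 doses.

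**Working it through.** **Inputs.** The documents give no AE rates and no Group A size. SAP 3.2 anticipates 50–80 patients for Groups A and B together. N, a and b below are therefore assumptions, and there is no figure in the plan to reproduce.

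**Formula.** Let a and b be the affected Group A patients in the 201 and 202 blocks. Cumulative count = a + b − overlap. The overlap lies between max(0, a+b−N) and min(a, b), so

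max(a, b) ≤ cumulative ≤ min(N, a+b).

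The width equals min(a, b) when a+b ≤ N. An enumeration for N=40, a=16, b=12 confirmed that all 13 integers from 16 to 28 are attainable. The last column, 1−(1−a/N)(1−b/N), is for reference only.

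| N | a | b | Lower | Upper | If independent |
|---|---|---|---|---|---|
| 50 | 2 | 2 | 2 (4%) | 4 (8%) | 7.8% |
| 50 | 5 | 5 | 5 (10%) | 10 (20%) | 19% |
| 50 | 10 | 10 | 10 (20%) | 20 (40%) | 36% |
| 50 | 15 | 10 | 15 (30%) | 25 (50%) | 44% |
| 50 | 15 | 15 | 15 (30%) | 30 (60%) | 51% |
| 40 | 16 | 12 | 16 (40%) | 28 (70%) | 58% |

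At 20% per block the range is 6–12 of 30, 10–20 of 50 or 14–28 of 70 patients.

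**Where there is no gap.** If either block is 0, the bounds meet: a=0, b=3 gives exactly 3. Deaths in 201 must be zero, because everyone tabulated was later dosed in 202. Discontinuations in 201 should be zero or nearly so, because Protocol 5.1 requires completion of 201 Visit 8. Those rows, and essentially all of Table 14.3.1.5, are already exact. Table 14.3.1.1 also gives event counts, which can be added across blocks.

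**Severity rows.** The bounds apply to rows that count any occurrence. Where a patient is placed at the highest severity, someone mild in 201 and severe in 202 would leave the mild row of a cumulative count, so for mild and moderate rows even the lower bound need not hold.

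**Length of a cumulative window** (nominal, before the ±7-day visit windows):

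- 201 block: 182 + 10 = 192 days (187–197 with the ±5 days).
- 202 block to Visit 6: 210 days.
- Total: 402 days (397–407), or 402/7 = 57.4 weeks.
- Off drug: 10 + 28 = 38 days (33–43). 38/402 = 9.5%, with a range from 33/397 = 8.3% to 43/407 = 10.6%.

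**Dosing tables.** If the 7-dose rule is applied, the lowest compliance possible in the PPS is 175/182 = 96.2% (168/175 = 96.0% and 182/189 = 96.3% at the ends of the Visit 5 window).

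**The case against.** The layout meets the protocol. Protocol 9.5.1 asks for descriptive tables over time, and a split at the 202 first dose provides that. SAP 9.1 discloses the assignment and carry-over rules and lists every AE by patient for both studies. Dosing stops for 10±5 days between the studies, so separate periods are defensible. The study is small, unpowered and tests no safety hypothesis. For a rare term, such as 2 of 50 in each block, the uncertainty is 2 patients. All of this stands, and it is why the remedy is an added column and the split stays.

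A cumulative column also carries a risk. Group A in 202 is selected: these patients completed 201 Visit 8, had an NRS increase of at most 2, and had no 201 finding that the investigator judged to preclude entry. A percentage counted from the first 200 mg dose could be taken for incidence among everyone who started 200 mg. It would also cover about 57 weeks rather than 52. Both objections stand, so the new column itself needs footnotes.

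On the dosing tables, SAP 7.9 explains why withdrawn patients have no compliance figure, and ITT compliance is listed for the rest. Moving Table 14.1.9 to the SAF therefore adds only non-withdrawn patients with major deviations. SAP 5 also leaves each patient's set assignment to a data review meeting, so the 96% floor is conditional. This part is secondary.

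A reader might infer more than the documents support:

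- *That the SAP contradicts the protocol.* It does not, for the reason above.
- *That the SAP keeps the 26+26-week period for an exploratory measure*, because SAP 8.3.8 uses it for the Group A biomarkers. The laboratory shift tables, which serve a primary endpoint, also span all 200 mg visits. The AE tables are the inconsistent part of the safety summaries.
- *That every row is affected, or that data are lost.* Rows with an empty block are exact, and the listings hold what is needed.

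**Conclusion.** The point holds for AE rows populated in both blocks: any AE, related AEs, the severity rows, system organ classes and the commoner preferred terms. For these, the planned tables give no once-per-patient incidence over the period named in the primary objective. When both blocks have equal counts and a+b does not exceed N, the upper bound is twice the lower. The percentages shown rest on assumed rates and an assumed Group A size; the bounds themselves do not.

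The gap is one of presentation, since nothing is left uncollected or unlisted. It should still be fixed, because it concerns the first-listed primary endpoint and the remedy is cheap. The pooled 201 Overall column and the use of the PPS for the dosing tables are real but smaller faults.

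**What to change.** (a) Add to Tables 14.3.1.1–14.3.1.4 and 14.3.1.6 a column *Group A, cumulative from first 200 mg dose in 201 to Visit 6 of 202*. Count each patient once per row, at the highest severity in severity rows. Table 14.3.1.5 does not need it.

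Footnote this column and the 201 columns to say that they cover only patients who completed 201 Visit 8 and rolled over, so they are not incidence among all who started 200 mg, and refer to the 201 report for the full arm. Footnote the cumulative column to say that it includes the off-drug 10±5-day gap and the 4-week follow-up.

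(b) Drop the 201 Overall column.

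(c) Secondary: run Tables 14.1.8 and 14.1.9 on the SAF. Count withdrawn patients in 14.1.8, but leave them out of the compliance percentage because the database does not hold the date of their last dose.

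The cost is SAP and shell wording plus programming on data the SAP already lists. The downside is slightly wider AE tables and possibly less favourable dosing figures.
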